**Association between signal intensity gradient of cerebral arteries from time-of-flight
magnetic resonance angiography and clinical outcome in patients with lenticulostriate
infarction: A multicenter retrospective cohort study**

Date of the document: August 5th 2020

Study population

This study is a multi-center, retrospective cohort study for all consecutive patients. From January 2015 to March 2021, patients who were diagnosed with acute ischemic stroke in the lenticulostriate artery (LSA) territory were registered at three centers (Jeonbuk National University Hospital, Samsung Medical Center, and Gunsan Medical Center). The 3 centers have their own characteristics: Gunsan Medical center is in a small city where about 300,000 citizens live, Jeonbuk National University Hospital is in a medium sized city where about 650,000 citizens live, and Samsung Medical Center is in a capital city where about 10,000,000 citizens live).

The inclusion criteria were as follows: (1) Patients aged 18 years or older who had brain magnetic resonance imaging (MRI) for acute ischemic stroke within 3 days, (2) Patients who underwent diffusion-weighted imaging (DWI) and apparent diffusion coefficient of the cerebral parenchyma, and cerebral angiographic measurements, in which, intracranial arteries should be examined by time-of-flight (TOF) techniques, and (3) A patient with high signal intensity lesions in the unilateral LSA territory on DWI.

The exclusion criteria are as follows. (1) Patients younger than 18 years of age, (2) Patients with moderate to severe ($>50\%$) stenosis or occlusion of the major intracranial and extracranial arteries, including internal carotid artery (ICA), middle cerebral artery (MCA), anterior cerebral artery (ACA), posterior cerebral artery (PCA), basilar artery (BA), and vertebral artery (VA), (3) Patients whose ischemic stroke was due to or related with cardiac or rare etiology (e.g., arterial dissection, moyamoya disease). The present study was conducted following approval from the ethics review committee in each hospital.

Acquisition of clinical data

Demographic and clinical information on cardiovascular risk factors (hypertension, diabetes mellitus, hyperlipidemia, and smoking history), laboratory findings at admission (including complete blood count, lipid profiles, serum glucose level, HbA1c) were extracted from electronic medical records. A neurological severity in each patient was monitored using National Institute of Health Stroke Scale (NIHSS) and modified Rankin Scale (mRS) during hospitalization, and were collected.

Clinical outcome

As a clinical outcome of the patients with the LSA infarction, mRS of discharge or 7th day was used to define clinical status: mRS 2 or less was defined as a good outcome group and 3 or more as a poor outcome group.

Time of Flight Magnetic Resonance Angiography

The MRA protocols in 3 hospital were described in detail, as in supplementary table 1. We used a 3.0T MR of a SENSE 32 Channel cardiac coil (Philips Medical Systems, Achieva, The Netherlands) to obtain a three-dimensional intracranial and extracranial TOF image. The parameters used to obtain TOF-MRA are as follows. TR = 23.0ms, TE = 3.5ms, Resolution = 300X220, FOV (field of view) = 180 mm², 160 slices, FA (flip angle) = 20.0°, scan duration = 1 minute 53 seconds – needs to be rewrite

Measurement of TOF MRA SIG from cerebral arteries

TOF MRA SIGs from cerebral arteries (both ICA, MCA, ACA, PCA, VA and one BA) were measured with a semi-automated software (VINT, Mediimage, Inc. Seoul, Republic of

Korea), as reported previously.¹ In brief, the signal intensities at the iso-point (Φ_a ; *signal intensity at position A [Xa] along the arterial contour line*) and at the inner point (Φ_b ; *signal intensity at position B [Xb]*) were calculated by using a trilinear interpolation algorithm based on the positions and signal intensities in the eight neighboring voxels. The signal intensities of TOF-MRA were normalized to eliminate the offset and scale effects across the MRA datasets of participants. For each iso-point (position A), the SIG was calculated from the difference in signal intensities between points A and B as follows:

$$\text{SIG, SI/mm} = (\Phi_b - \Phi_a) / |X_b - X_a| \quad (1)$$

The mean values of SIG of cerebral arteries were obtained, as shown in Figure 1. The arterial SIG measurement was performed in the straight segment as possible in ICA (at the C1 distal portion before a horizontal intrapetrous segment), VA (V4 distal, just before a conjoined BA), and BA (mid to distal portion). For the MCA and ACA, the initial 1/2 or 1/3 segment was chosen. For the PCA, P2 segment (distal to posterior communicating artery) was selected for a measurement.

Statistical analysis

Descriptive data for the clinical characteristics and laboratory findings of the participants were expressed as a mean \pm standard deviation or percentage as appropriate. Kolmogorov-Smirnov test was performed for distributional adequacy. A student t-test or chi-square test was used to assess differences as appropriate. Logistic regression analyses were performed to determine the independent association between the SIG values in cerebral arteries and favorable outcome, adjusting for all possible confounders. Statistical analyses were conducted using SPSS version 20 (SPSS, Chicago, IL, USA).

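### Does the missing day zero for the day-7-or-discharge mRS leave the outcome too loosely defined to analyse?

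*Combined protocol and SAP*

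**What the plan says.** The Clinical outcome section of the combined protocol and SAP defines one outcome: "mRS of discharge or 7th day was used to define clinical status". The cut follows: "mRS 2 or less was defined as a good outcome group and 3 or more as a poor outcome group". NIHSS is also collected but is not named as an outcome.

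The Acquisition of clinical data section places the scale in the hospital stay: "A neurological severity in each patient was monitored using National Institute of Health Stroke Scale (NIHSS) and modified Rankin Scale (mRS) during hospitalization". It lists no assessment days. The one starting event named in that section belongs to the blood tests: "laboratory findings at admission (including complete blood count, lipid profiles, serum glucose level, HbA1c) were extracted from electronic medical records".

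The only other time window is inclusion criterion 1 under Study population, which requires "brain magnetic resonance imaging (MRI) for acute ischemic stroke within 3 days". That window has no stated starting event either.

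The Statistical analysis section uses the outcome class in logistic regression to estimate the "independent association between the SIG values in cerebral arteries and favorable outcome". It does not restate the scoring time, and it names no covariate for scoring day or length of stay.

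**The concern.** Three things are left unsaid: the event from which the seventh day is counted, whether that day is numbered 0 or 1, and which score prevails for a patient who has both a day-7 and a discharge value. Function can change quickly in the first days after a stroke, and the outcome is cut between 2 and 3, so a different scoring day could move a patient from one group to the other. Two people reading the same chart could in principle record different classes. The class is the dependent variable of the only multivariable analysis, and the data come retrospectively from the records of three hospitals. A dependent variable without a fixed time of measurement is therefore a reasonable thing to question.

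**Working it through.** The plan states no sample size, event count or effect size for this outcome, so there is no figure of its own to reproduce. The check is a reading of the text plus day counting.

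**Step 1: precedence.** The scale is recorded in hospital only. A patient discharged on day 4 then has no day-7 score and must be scored at discharge. For a patient who stays longer, naming day 7 at all makes sense mainly if it caps the scoring time. The alternative, discharge first with day 7 as a fallback, would bring day 7 into play mostly when a discharge score is missing, since everyone discharged alive has a discharge point. Day 7 or earlier discharge is the natural reading.

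**Step 2: the count on that reading.** For an in-hospital scale the natural clock is the hospital stay.

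- Admission is day 1: the seventh day is 7 − 1 = 6 days after admission.
- Admission is day 0: it is 7 days after admission.
- Difference: 7 − 6 = 1 day.

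**Step 3: onset as a rival origin (illustration).** Let k be the days from onset to admission. Assume that the 3-day imaging window runs from onset and that the scan is done on or after admission, so k is at most 3. The plan states neither. The seventh day, in days after admission, is then:

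| k | onset = day 1 (6 − k) | onset = day 0 (7 − k) | admission = day 1 | admission = day 0 | spread (1 + k) |
|---|---|---|---|---|---|
| 0 | 6 | 7 | 6 | 7 | 1 |
| 1 | 5 | 6 | 6 | 7 | 2 |
| 2 | 4 | 5 | 6 | 7 | 3 |
| 3 | 3 | 4 | 6 | 7 | 4 |

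At k = 3 the four candidates fall 6, 7, 9 and 10 days after onset.

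**Step 4: the scan as a further origin.** If the scan is m days after onset, with k ≤ m ≤ 3, it adds candidates at 6 + m and 7 + m days after onset. The spread becomes (7 + m) − 6 = 1 + m, which is still at most 4 days. If the imaging window runs from admission instead, the documents put no limit on the delay from onset.

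**Step 5: what these spreads measure.** They are distances between rival conventions for one patient. They are not variation shown within this study. Under any one convention, each patient still in hospital has one scoring day.

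**Step 6: when a class would change.** Two conditions must both hold: the patient is still in hospital on the earlier candidate day, and the mRS crosses from 2 to 3, or back, before the later one. Patients discharged before the earlier candidate day have the same score under every convention compared here. The documents give no length of stay, no delay from onset to admission and no serial mRS, so the number of such patients cannot be computed.

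**The case for a change.** The strongest reply is that taking the earlier of discharge and day 7 settles precedence but not the count: the rule cannot be applied until day 7 is a date, and nothing in the plan supplies one. Three hospitals of different character extract scores after the fact, so each could use its own convention without anyone noticing. The regression names no adjustment for scoring day. Stating the origin would take a sentence.

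The silence of the text stands, and anyone wishing to reproduce the outcome would need to know the convention used. It is also true that a discharge-first rule would have no upper limit on the scoring day, so the spreads of 1 to 4 days do not cover that reading.

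The rest does not carry the point to a change. No described procedure shows differing conventions between hospitals or abstractors; that is a possibility only. The absence of onset date from the listed data fields is no evidence about the origin, because admission date, discharge date and mRS assessment dates are not listed either. The discharge-first reading is strained for the reason given in step 1. Choosing an origin is also a matter of preference: counting from admission scores late arrivals later after onset, and counting from onset scores them earlier in their stay. Finally, patients discharged before day 7 are scored at varying times whichever origin is written down. That larger source of uneven timing comes from using an in-hospital outcome in a retrospective cohort, and naming a day zero would not remove it.

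**Conclusion.** No change to the plan is called for. The definition is terse, but it is a gap that analysts fill sensibly: hospital day 7, or discharge if sooner. On that reading the remaining ambiguity is 1 day, 6 versus 7 days after admission, and it matters only for a patient still in hospital who crosses the cut within that day. Spreads of 2 to 4 days need a rival origin and assumptions the plan does not make. No direction or size of effect on the SIG odds ratio has been shown, and none can be derived from the documents.

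This conclusion rests on two assumptions: that the natural reading is the one used, and that one convention is applied across the three hospitals. Evidence that the hospitals counted from different events, or that discharge scores were used for patients staying well beyond a week, would reopen the question. The plan contains no such evidence.

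### Poor outcome is an absolute mRS of 3 or more, and pre-stroke mRS is neither an exclusion nor a listed data item, so patients already dependent before the stroke are very likely counted as poor outcomes

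*Combined protocol and SAP*

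**What the plan says.** - **Clinical outcome.** The timing is given as "mRS of discharge or 7th day was used to define clinical status", and the split is "mRS 2 or less was defined as a good outcome group and 3 or more as a poor outcome group". Neither sentence refers to the patient's function before the stroke.
- **Study population.** The design is a "multi-center, retrospective cohort study for all consecutive patients". Apart from age under 18, the exclusions are more than 50% "stenosis or occlusion of the major intracranial and extracranial arteries", and "Patients whose ischemic stroke was due to or related with cardiac or rare etiology". None concerns prior disability.
- **Acquisition of clinical data.** Demographics, four vascular risk factors and admission laboratory values "were extracted from electronic medical records". Severity is followed with NIHSS and "modified Rankin Scale (mRS) during hospitalization, and were collected". Pre-stroke mRS and prior stroke are not listed.
- **Statistical analysis.** Logistic regression is to estimate the independent association of SIG with favorable outcome, adjusted for every possible confounder. No covariate is named.

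**The concern.** The mRS measures overall disability, whatever its cause. Someone who was at mRS 3 or more before admission is very unlikely to be at 2 or less within days of a new infarct. Under the stated split that patient is a poor outcome almost by definition, and SIG had no opportunity to predict anything.

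Two consequences are possible, and they differ in kind:

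- If prior dependence is unrelated to SIG, the extra poor outcomes are noise. A true association is diluted and some power is lost.
- If dependent patients also tend to have lower SIG, beyond what the adjustment variables explain, the model can show an association when SIG has no bearing on recovery from this infarct.

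If the adjustment variables do explain the link, the false association largely disappears. Without pre-stroke mRS, a reader cannot tell which case applies. The listed data hold only indirect information: age, the risk factors, and in-hospital NIHSS and mRS. The last two already reflect the new stroke, so they cannot separate an old deficit from a new one.

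**Working it through.** **Inputs.** The outcome definition, enrolment rule, exclusions and data list come from the documents. Everything numerical below is assumed, because the documents give no sample size, event rate, dependence rate or SIG difference, and there is no figure of the plan's own to reproduce. Let q be the share with pre-stroke mRS 3 or more (2%, 5%, 10%), all taken to stay at 3 or more, and p the poor-outcome rate among the others (20% or 30%).

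**Step 1: share of the poor group already dependent.** Formula: q / (q + (1 − q)p). For q = 0.05 and p = 0.30: 0.05 / (0.05 + 0.95 × 0.30) = 0.05 / 0.335 = 15%.

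| p | q = 2% | q = 5% | q = 10% |
|---|---|---|---|
| 30% | 6% | 15% | 27% |
| 20% | 9% | 21% | 36% |

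**Step 2: dilution when dependence is unrelated to SIG.** Take a true odds ratio of 2.0 for low versus high SIG, with p the poor rate in the high-SIG group. At p = 0.30 the low-SIG odds are 2 × 0.30/0.70 = 0.857, a risk of 0.4615. Adding q = 5% to both groups gives risks of 0.05 + 0.95 × 0.4615 = 0.4885 and 0.05 + 0.95 × 0.30 = 0.335. The odds are 0.955 and 0.504, and their ratio is 1.90.

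| p | q = 2% | q = 5% | q = 10% |
|---|---|---|---|
| 30% | 1.96 | 1.90 | 1.81 |
| 20% | 1.93 | 1.83 | 1.71 |

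**Step 3: power.** Simulation with 300 patients, 30% poor among the others, an odds ratio of 0.70 per SD of SIG, no link between dependence and SIG, a logistic model of outcome on SIG and age, and a two-sided 5% Wald test. At q = 2%, 5%, 10%, power is 76%, 73%, 66% in all patients and 78%, 77%, 75% when restricted to patients not previously dependent.

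**Step 4: false association when dependence is related to SIG.** Same simulation with no true SIG effect. Dependent patients are 1 SD higher on an age-like covariate and have lower SIG, with none, half or all of the SIG gap carried by age. There are 6,000 datasets per cell, with a Monte Carlo error of 0.3 to 0.6 points. Type I error of the age-adjusted all-patient model:

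| SIG gap | Explained by age | q = 2% | q = 5% | q = 10% |
|---|---|---|---|---|
| 0.5 SD | half | 4.5% | 5.5% | 8.0% |
| 0.5 SD | none | 5.5% | 9.7% | 17.2% |
| 0.25 SD | half | 5.1% | 5.7% | 5.6% |
| 0.25 SD | none | 4.9% | 5.9% | 8.5% |
| either | all | about 5% | about 5% | about 5% |

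The restricted model stays at 4-5% in every cell. Repeats of the worst row gave 8.7% and 9.4% at q = 5%, and 17.4% and 17.9% at q = 10%.

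**Step 5: a severity covariate.** The plan also collects NIHSS. With an NIHSS-like covariate in the model (assumed 1 SD higher in dependent patients, log odds ratio 1 per SD in the others), the 0.5 SD gap that age does not explain gives about 6-7% at q = 5% and about 11% at q = 10%. Severity adjustment therefore absorbs part of the problem but not all of it at 10%.

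**The case against.** The strongest reply has four parts.

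1. **The plan lists no covariates.** A reader might infer that the adjusted model leaves out pre-stroke mRS. The documents do not support that. The commitment to adjust is open-ended and nominally covers it, so the variable is unlisted rather than ruled out. What stands is narrower: a model cannot adjust for a field that was not abstracted, and this one is absent from the data list.
2. **Collected variables carry some of the information.** This is right for age, risk factors, NIHSS and in-hospital mRS, and Step 5 shows that an age-only calculation can overstate the inflation. They remain partial proxies.
3. **The largest figure is a corner case.** A type I error near 17% needs 10% dependent, a 0.5 SD gap, nothing explained by age and no severity covariate. Nothing in the documents shows that dependence is linked to SIG, and the exclusions for large-artery and cardiac or rare causes may lower the share of dependent patients, though they do not remove them. This stands, and the milder cells should carry the weight.
4. **The all-patient analysis is a legitimate target.** The plan says the mRS defines clinical status, not disability caused by this infarct. A reader might infer that the all-patient model is wrong; it is not. It answers a broader question, and the plan lacks the means to answer the narrower one beside it.

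**Conclusion.** The point holds as a gap in data and sensitivity analysis, not as a demonstrated bias. The absolute outcome split, the absence of an exclusion for prior disability and the missing pre-stroke mRS are all plain in the text. That previously dependent patients would be counted as poor outcomes follows almost directly.

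The size is unknown. On the assumed inputs it is near negligible at 2% dependent. At 5% to 10%, with 30% poor among the others, it is modest dilution if dependence is unrelated to SIG. If half of a 0.5 SD SIG gap is explained by age, type I error is about 6% to 8%. It rises to about 10% and 17% only if age explains none of that gap, and is lower with a severity covariate. A reader might take the 17% as the expected error rate of this study; no document figure supports that. The improvement is worth making because it is cheap and would show which case applies.

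**What to change.** - Abstract pre-stroke mRS from the same electronic records.
- Report by centre how many patients have pre-stroke mRS 3 or more, and how many have it unrecorded. If few are dependent, that count largely closes the question.
- Keep the all-patient model.
- Add, as a prespecified sensitivity analysis, the same adjusted logistic model restricted to pre-stroke mRS 0-2, once with unrecorded patients left out and once with them left in.
- If pre-stroke mRS is also entered in the all-patient model, use the ordered score. An indicator for 3 or more would predict poor outcome almost perfectly and destabilise the fit.
- State what each model addresses: the all-patient model, overall clinical status; the restricted model, outcome more attributable to this stroke. Restriction may remove part of an association that runs through chronic vascular disease.

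**Cost.** One more field per chart, and a small loss of patients in the restricted model (of 300: 6, 15 or 30 at 2%, 5%, 10% dependent). Some values in 2015-2021 records will be unrecorded. If 20% are unrecorded completely at random, restricted power is 68%, 67%, 64% with those patients left out, no better than the all-patient 76%, 72%, 67% in the same runs, and 77%, 75%, 73% with them left in. That is why both versions are needed. Missingness in retrospective charts may well not be random, and the report should say so. If the field cannot be retrieved, that should be stated as a limitation.
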